9.0 REPORTING AND MONITORING

9.1 Statement of Compliance

This trial will be conducted in compliance with the appropriate protocol, appropriate ICH guidelines (including current Good Clinical Practice [GCP]), the principles of the Declaration of Helsinki, and all other applicable regulatory requirements. The study team must obtain written approval of the study protocol, consent form, other supporting documents, and any advertising for participant recruitment from the UT Southwestern institutional review board (IRB) in order to participate in the study. Prior to study initiation, the protocol and the informed consent documents will be reviewed and approved by an appropriate Ethics Review Committee (ERC) or IRB. Any amendments to the protocol or consent materials must be approved before they are implemented. Annual progress reports and Serious Adverse Event (SAE) reports will be submitted to each IRB, according to its usual procedures.

9.2 Regulatory Files

The regulatory files should contain all required regulatory documents, study-specific documents, and all important communications. Regulatory files will be reviewed at each participating site for regulatory document compliance prior to study initiation, throughout the study, as well as at the study closure.

9.3 Informed Consent

The informed consent form is a means of providing information regarding the trial to a prospective participant and allows for an informed decision about participation in the study. The informed consent will be approved by their IRB(s). Every study participant is required to sign a valid, IRB-approved current version of the study informed consent form prior to the initiation of any study related procedures. The original signed informed consent for every participant will be stored in a locked, secure location that is in compliance with their IRB and institutional. Every study participant must be offered a copy of the signed consent form. Participants may contact site personnel with any questions after signing Informed Consent.

Prior to signing the informed consent form, research staff who are knowledgeable about the study will explain the study to the potential participant and provide the participant with a copy of the consent to read. If the participant is interested in participating in the study, a researcher who is authorized to obtain informed consent will review each section of the informed consent form in detail, answer any of the participant's questions, and determine if the participant comprehends the information provided by administering the comprehension tool. The participant will consent by signing and dating the consent document. The person obtaining consent will also sign and date the consent document. The consent must be properly executed and complete to be valid. It is strongly recommended that another research staff member review the consent after it is signed to ensure that the consent is properly executed and complete. All persons obtaining consent must have completed appropriate training.

The informed consent form must be updated or revised whenever important new safety information is available, or whenever the protocol is amended in a way that may affect a participants' participation in the trial. A copy of the informed consent will be given to a prospective participant to review during the consent process and to keep for reference. The participant will be informed that their participation is voluntary and they may withdraw from the study at any time, for any reason without penalty.

Study participation is voluntary and there are no benefits lost if an individual declines participation. Individuals who refuse to participate or who withdraw from the study will be treated

without prejudice. Study sites will be responsible for maintaining signed consent forms as source documents for quality assurance review and regulatory compliance.

Participants will be offered copies of the signed informed consent form, and the originals will be stored in a secure location at each study site. Contract and local monitors will inspect the informed consent forms periodically to ensure that correct signatures and dates were obtained on valid informed consent forms prior to any study interventions.

9.4 Health Insurance Portability and Accountability Act (HIPAA)

Study sites may be required by their institutions to obtain authorization from participants for use of protected health information. Sites will be responsible for communicating with their IRBs or Privacy Boards and obtaining the appropriate approvals or waivers to be in regulatory compliance.

9.5 Release of Information

Study participants will be asked to sign a release of information form that will give study staff permission to seek and acquire their treatment records. This release of information is voluntary. There will be no benefits lost if study participants refuse to release information. They may continue to participate in the study.

9.6 Study Documentation

Study documentation includes all case report forms, data correction forms, workbooks, source documents, monitoring logs and appointment schedules, sponsor-investigator correspondence, and signed protocol and amendments, Ethics Review Committee or Institutional Review Committee correspondence and approved consent form and signed participant consent forms.

Source documents include all recordings of observations or notations of clinical activities and all reports and records necessary for the evaluation and reconstruction of the clinical research study. Whenever possible, the original recording of an observation should be retained as the source document; however, a photocopy is acceptable provided that it is a clear, legible, and exact duplication of the original document.

9.7 Records Retention and Requirements

All research records for all subjects will be stored by the investigator in a secure location to be accessed only by authorized research personnel. Study records will be stored in accordance with local IRB, State, and Federal Regulations but, in any case, will be kept for a minimum of 7 following study completion.

9.8 Safety Monitoring

9.8.1 Data and Safety Monitoring

Drs. [name] and [name] will meet weekly to examine accumulating data to assure protection of participants' safety while the study's scientific goals are being met. These meetings will determine whether there is support for continuation of the trial, or evidence that study procedures should be changed, or if the trial should be halted, for reasons relating to the safety of the study participants, the efficacy of the treatment under study, or inadequate trial performance (e.g., poor recruitment).

9.8.2 Protocol Violations Reporting and Management

A protocol departure is any departure from procedures and requirements outlined in the protocol. Protocol departures may occur on two levels, deviation versus violation. The difference between a protocol deviation and violation has to do with the seriousness of the event and the corrective action required. A protocol deviation is considered an action (or inaction) that by itself

is not likely to affect the scientific soundness of the investigation or seriously affect the safety, rights, or welfare of a study participant. Protocol violations are departures that may compromise the participant safety, participant rights, inclusion/exclusion criteria or study data and could be cause for corrective actions if not rectified or prevented from re-occurrence. Protocol violations will be monitored for (1) significance, (2) frequency, and (3) impact on the study objectives, to ensure the integrity of the trial. The PI or designee will make the decision about whether a departure from the protocol will be designated as a protocol deviation or a protocol violation. All protocol violations and deviations will be reported to the IRB as required.

9.8.3 Subject Confidentiality/Privacy

Participant records will be held confidential by the use of study codes for identifying participants on CRFs, secure and separate storage of any documents that have participant identifiers, and secure computing procedures for entering and transferring electronic data.

All research information obtained on participants is confidential, and disclosure to any third parties without specific authorization is strictly prohibited. To maintain subject privacy, all study forms and reports will be identified by a coded study identification number only. No subject identifying information will be included in any presentations or publications resulting from the study.

Study records may be inspected by the sponsor and its authorized representatives, other government agencies such as the U.S. Department of Health and Human Services (DHHS) Office for Human Research Protections (OHRP), authorized Node Staff, or the local IRB for quality assurance purposes.

9.8.4 Adverse Events (AEs) and Serious Adverse Events (SAEs)

The Primary Investigator (PI) may appoint a Study Clinician (MD, PhD, or PI) for this study, who will review or provide consultation for each Serious Adverse Event (SAE) as needed. These reviews will include an assessment of the possible relatedness of the event to the study intervention or other study procedures. The Study Clinician will also provide advice for decisions to exclude, refer, or withdraw participants as required. The study staff will be trained to monitor for and report Adverse Events and Serious Adverse Events.

9.8.5 Definitions of Adverse Event and Serious Adverse Event

Standard definitions for Adverse Events and Serious Adverse Events, their identification, characterization regarding severity and relationship to the study intervention and processing are described in Appendix 1.

9.8.6 Non-Reportable Adverse Event and Serious Adverse Events

Adverse Events

For the purpose of this study, the following AEs will not require reporting in the data system and will not be captured:

- Grade 1 (mild) unrelated event.
- Grade 2 (moderate) unrelated event.

This would typically include physical events such as headache, cold, etc that was considered unrelated to study participation by the PI.

Serious Adverse Events

For the purpose of this study, the following SAEs will not be recorded in the data system but will be documented:

- Admission to a hospital/surgery center for preplanned/elective surgeries (captured in the Visit Summary/Progress Note).
- Admission to a hospital for scheduled labor and delivery (captured in the Visit Checklist/Progress Note).

Local documentation and reporting guidelines should also be followed based on IRB requirements.

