1.0 BACKGROUND

The over 2.9 million breast cancer survivors in the United States face significant post-treatment health burdens. Five-year recurrence rates for Stage I-III breast cancer survivors range from 7-13%¹ and a subset of breast cancer survivors (e.g., BRCA1/2 mutation carriers) may also have increased risks for other cancers.² Breast cancer survivors have significant medical comorbidities, symptom burdens, and late effects that decrease quality of life and affect prognosis.³ Substantial gaps remain in our understanding of how to improve prognosis for this rapidly growing population. Depression and physical inactivity are inter-related, but modifiable, risk factors associated with prognosis among breast cancer survivors. The proposed pilot project will assess the implementation of evidence-based strategies for increasing physical activity among breast cancer survivors. **Successful completion of project aims will result in crucial pilot data to support future grant applications to identify optimal strategies for increasing physical activity in breast cancer survivors.**

Depression and Cancer Prognosis. **Depression is a common comorbidity in breast cancer survivors and an important factor associated with poor prognosis.** Individual studies estimate the prevalence of Major Depressive Disorder (MDD) in breast cancer survivors to range from 10-30%.⁴ When including dysthymia and minor depression, the rates of mood disorders in breast cancer survivors are estimated to be as high as 50%.^{5,6} **More importantly, depressive symptoms are linked to higher rates of mortality among breast cancer survivors.** A recent meta-analysis integrated 76 prospective studies, including those in which depression was assessed prior to cancer diagnosis and those that assessed depression after diagnosis. Results indicated an 18% increase in mortality for breast cancer patients with depression.⁷ Conversely alleviation of depressive symptoms in breast cancer patients is associated with longer survival,⁸ suggesting the importance of evidence-based interventions targeting depression.

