5.3 Baseline

Potential subjects will meet with a trained project interventionist to be assessed for safety of engaging in physical activity, following recommendations identified in the ACSM guidelines.¹⁸ The Physical Activity Readiness Questionnaire (PAR-Q)¹⁹ is a self-report questionnaire designed to assess safety of engaging in physical activity. In addition, lymphedema and pain will be assessed at baseline and throughout the program to ensure participant safety. Subjects will also be instructed to contact their physician to ensure their safety engaging in physical activity.

Study assessments (described in section 6.0) will be conducted at the baseline assessment visit. Participants will complete the PAR-Q to identify potential medical contraindications. Participants indicating potential contraindications to exercise will be instructed to discuss participation with their physician before engaging in physical activity.

Blood samples will be collected at the baseline assessment visit.

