6.2.5 Safety Assessments

Assessments involved in determining participants' ability to safely participate in the protocol (maximal exercise testing, laboratory tests, and physical exam) are described under Diagnostic

and Screening Measures. Additionally, reportable AEs and all SAEs will require completion of an AE Form (and SAE form as applicable) to document and track reportable AEs.

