1.0 Definitions of Adverse Events and Serious Adverse Events

1.1 Adverse Event (AE)

An adverse event (AE) is defined as any reaction, side effect, or untoward event including any new illness, symptom, sign or worsening of a pre-existing condition or abnormality that occurs during the course of an individual's participation in a clinical trial, *whether or not* the event is considered related to the clinical trial intervention.

Stable chronic conditions, such as arthritis, which are present prior to an individual's enrollment in a clinical trial and that do not worsen during the course of their participation are not considered AEs. In order to avoid the reporting of pre-existing conditions as new AEs, and to assist with the assessment of a condition that may have worsened in intensity or severity, a thorough medical history should be performed during the eligibility assessment phase to record any chronic, acute, or intermittent preexisting or current illnesses, diseases, symptoms, or laboratory signs.

An AE case report form (CRF) is used to capture reported AEs (as defined by the protocol) and may also be used to record follow-up information for unresolved or ongoing events that were reported previously.

A site study investigator is responsible for reviewing and characterizing each AE that is reported, and is expected to follow appropriate reporting procedures.

Adverse events and their resolution outcome should be elicited from study participants at each study related contact. The site must actively seek information about the AE until it is resolved or medically stable or until the participant is lost to follow-up and terminated from the study.

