1.3 Pregnancy

All pregnancies that are reported during the course of the clinical trial will be captured on a Visit Checklist/Progress Note and not separately reported as an AE or SAE. Pregnancies will be followed through resolution, regardless of the outcome.

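### Section 9.8.6 requires no AE record for Grade 1-2 events judged unrelated, and makes no exception for lymphedema and pain, the two symptoms that 5.3 singles out for safety assessment

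*Combined protocol and SAP*

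**What the plan says.** Section 9.8.6 lists two classes of non-reportable adverse event, Grade 1 unrelated and Grade 2 unrelated, and says that "the following AEs will not require reporting in the data system and will not be captured". Relatedness is the principal investigator's call, and the examples given are headache and cold. No event type is excepted.

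Two other exemptions are worded differently. For planned surgery and scheduled delivery admissions, 9.8.6 says that "the following SAEs will not be recorded in the data system but will be documented", and it names the note to be used for each. Under Appendix 1, section 1.3, pregnancies are "captured on a Visit Checklist/Progress Note and not separately reported as an AE or SAE".

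Section 5.3 singles out two symptoms: "lymphedema and pain will be assessed at baseline and throughout the program to ensure participant safety".

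The recording rules elsewhere follow the 9.8.6 definition. In section 6.2.5, "reportable AEs and all SAEs will require completion of an AE Form". In Appendix 1, section 1.1, the AE case report form "is used to capture reported AEs (as defined by the protocol"). The same section also says: "Adverse events and their resolution outcome should be elicited from study participants at each study related contact".

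**The concern.** The protocol picks out lymphedema and pain as matters to watch for safety, and then applies to them the same non-capture rule as to a cold. The background section says that "Breast cancer survivors have significant medical comorbidities, symptom burdens, and late effects", so some mild or moderate episodes may be put down to the cancer or its treatment. Grade 2 is not trivial in an activity program: by the Appendix 1 definition it can involve some limitation of activity.

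At stake is the safety record. The judgment that an event is unrelated also removes the requirement to record it. With one group and no comparator, the main ways to test such judgments are to re-read the individual cases or to look for a pattern across participants. Both need a record.

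**Working it through.** No formula applies and the plan states no figure on this point. The check is whether any other section restores a required record for a Grade 1-2 episode of lymphedema or pain judged unrelated.

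1. **Is the non-capture wording only shorthand for keeping the event out of the database?** Probably not. Within 9.8.6 the exempt SAEs are kept out of the data system but documented in a named note, and Appendix 1, section 1.3 does the same for pregnancy. The exempt AEs alone get no named note.

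2. **Do the AE forms restore a record?** No. Section 6.2.5 ties the AE form to reportable AEs and SAEs, and Appendix 1, section 1.1 ties the AE case report form to what the protocol defines as reported. Both lead back to 9.8.6.

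3. **Do the reporting procedures restore it?** No. In Appendix 1, section 4.0, both the 7-day reporting rule and the summary reports, made at least annually, are limited to reportable AEs.

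4. **Does the assessment schedule restore it?** No. The section 6.1 table has no lymphedema row and no separate pain row, and section 6 describes no lymphedema measure. The pain measure named there is the SF-36 pain domain, collected at baseline, Week 13 and Week 25. That is an outcome score, not a dated and graded event.

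5. **Which episodes can fall into the exemption?** Appendix 1, section 3.2 sets two conditions for an unrelated event: it lacks a reasonable temporal sequence after the intervention, and it is most likely explained by disease or other therapy. An event with a reasonable temporal sequence and a known response pattern, for which disease or another therapy is also a plausible cause, is possibly related and stays reportable at any grade. Attribution to the cancer alone is therefore not enough. What is left is Grade 1-2 episodes judged to meet both conditions. Such a judgment may be easier to reach after the 12-week program ends, and AE assessment runs on to the last visit, at Week 25.

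6. **Is the event seen before it is exempted?** Yes. AEs are to be elicited at every study contact, and the exemption cannot be applied until the event has been graded and judged for relatedness. The gap lies in the record, not in the asking.

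**The case against.** The strongest case against is that the rule is a deliberate and proportionate limit on burden in a 50-person pilot of print materials, an activity monitor, group sessions and optional facility access, and that it loses very little. Several parts of this stand.

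- The temporal condition means that many episodes arising during the program would be at least possibly related, and so recorded. A reader might infer that any lymphedema or pain attributed to the cancer or its treatment goes unrecorded. The section 3.2 definitions do not support that.
- Appendix 1, section 3.0 has an investigator review reported AEs weekly in order to characterize them. Reported there can fairly mean reported to staff, which would include events later exempted. The weekly safety meeting in 9.8.1 looks at accumulating data, not only AE forms. A reader might infer that the weekly review never sees these events. The documents do not establish that.
- The 5.3 assessments are planned, Appendix 1, section 2.0 has staff review progress notes and checklists after each contact, 9.6 treats clinical notations as source documents, and 9.8.6 defers to local IRB documentation rules. Source records may well exist. Section 7.2 refers to a Manual of Procedures and a Study Tools Manual, which are not among the documents, so how the 5.3 findings are written down is unknown.
- Section 5.3 names only lymphedema and pain. Extending the point to musculoskeletal injury would go beyond the signals the protocol chose.

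One thing is left unanswered. None of these provisions requires a dated, graded AE entry with the relatedness call for an exempted episode. Being seen once, at the time of the call, is not the same as being available for a later recheck or count.

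**Conclusion.** The point holds in a narrow form and is minor. Section 9.8.6 removes the required AE entry for new or worsening lymphedema or pain that is Grade 1-2 and judged unrelated, although 5.3 makes these two symptoms safety assessments. A later recheck of that call, or a tally across participants, then depends on unstructured records that may or may not be complete.

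Events at least possibly related and Grade 3 or higher events remain reportable. SAEs remain recorded, or documented in notes for the listed planned admissions. No planned efficacy or feasibility result is affected.

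The size cannot be given as a number, because the documents state no rate of lymphedema or pain and no rate of unrelated calls. The conclusion assumes that the non-capture wording means what it says and that the manuals add no structured log for these symptoms. If they do, the gap is already closed in practice and only the wording of 9.8.6 needs to match.

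**What to change.** Add one sentence to 9.8.6: new or worsening lymphedema and pain are exempt from the non-capture rule whatever the judged relatedness; each is logged with date, grade and relatedness, and included in the weekly review. All other unrelated Grade 1-2 events, such as colds and headaches, may stay exempt. Clinical management of these episodes is for the clinicians and is not changed.

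The cost is that sentence and a few extra AE entries, whose number cannot be estimated from the documents. No new contact or staff is needed, because AEs are already elicited at each contact and already have to be graded and judged before the exemption can apply.
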